All secondary outcomes assessed 14 months after baseline. In MyHC-T2D intervention arm, 14 months post baseline corresponds to approximately 12 months after the main component of the MyHC-T2D intervention.	
Hypoglycemia: % time glucose < 54 mg/dL, % time glucose < 70 mg/dL, # of events ≥ 15 minutes glucose 54-69 mg/dL, # events ≥ 15 minutes glucose < 54 mg/dL, # of events ≥ 15 minutes glucose < 70 mg/dL between 12 AM and 6AM
 
Hyperglycemia: % time glucose > 180 mg/dL, % time glucose > 250 mg/dL
 
Time in range: % time between 70 to 180 mg/dL
 
Glucose Management Indicator
 
Average glucose
 
Glucose variation: coefficient of variation, standard deviation
 
Self-reported measures: # of severe hypoglycemic events in prior 4 months: # of moderate hypoglycemia events in past 4 weeks; # of nocturnal hypoglycemic events in past 6 months; hypoglycemia unawareness; fear of hypoglycemia; diabetes knowledge; diabetes self-efficacy
 
Hemoglobin A1c
 
Hypoglycemia-related healthcare utilization: total number of urgent care, emergency department and inpatient visits for hypoglycemia as primary or principal diagnosis collected from the electronic health record (EHR)

Roles and Responsibilities

[name], MPH

Principal investigator and research physician

- Design and conduct of the study
- Preparation of protocol and revisions
- Overseeing and directing the study team and all implementation and data collection
- Leading Stakeholder Advisory Committee meetings
- Leading analyses and publication of study reports

Study Team:

Name, degree(s)	Role
[name], MS	Biostatistician
[name], MRCP (UK)	Consultant
[name], MS	Project Manager
[name], MA, MPH	Qualitative Research Associate
[name]	Patient partner and Co-Investigator
[name]	Family member partner and Co-Investigator
[name]	Qualitative Lead and Co-Investigator
[name]	Co-Investigator
[name]	Co-Investigator
[name], MS	Programmer Analyst
[name]	Implementation Lead and Co-Investigator
[name]	Endocrinologist
[name], BSc (Hons Biochem), [name], FRCP (Ed)	Consultant
[name]	Biostatistician and Co-Investigator
[name] CPsychol FFBPsS	Consultant
[name]	Family member partner and Co-Investigator
[name], MFA	Patient partner and Co-Investigator

Study team responsibilities:

- Agreement of final Study Protocol (*All*)
- Adaptation of MyHC-T2D; development and oversight of interventions (*EL, JN*)

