To determine if proactive care management plus MyHC-T2D is superior to proactive care management alone at preventing self-reported severe hypoglycemia in adults with type 2 diabetes at high risk for severe hypoglycemia. The primary outcome will be assessed through self-report via study survey at 14-months post baseline.

1b.2 Secondary objectives

1b.2.a Key secondary objectives

Key secondary outcomes will be assessed at 14-months post baseline through self-report in study survey (SR), continuous glucose monitors (CGMs; study participants will wear CGMs for 10 days), and electronic health records (EHRs).

1. To determine if proactive care management plus MyHC-T2D is superior to proactive care management alone in adults at high risk for severe hypoglycemia for the following:
 - Reducing percentage time with biochemical hypoglycemia (CGM assessed)
 - Reducing biochemical hypoglycemic events (CGM assessed)
 - Reducing the frequency of high blood sugars and reducing variability of blood glucose levels (CGM assessed)
 - Reducing number of severe hypoglycemic events in prior 4 months (SR assessed)
 - Reducing hypoglycemia unawareness (SR assessed)
 - Reducing number of self-reported moderate hypoglycemic events (SR assessed)

- Reducing fear of hypoglycemia (SR assessed)
- Reducing frequency of nocturnal hypoglycemia (SR assessed)
- Improving diabetes and hypoglycemia knowledge (SR assessed)
- Improving diabetes self-efficacy (SR assessed)
- Reducing hypoglycemia related healthcare utilization, including urgent care, Emergency Department and inpatient visits related to hypoglycemia (EHR assessed)

2. To assess differences in glycemic control, indicated by Hemoglobin A1c, between study participants in the proactive care management plus MyHC-T2D group and the proactive care management alone group.

1b.2.b Other secondary Objectives

Conduct a mixed methods process evaluation to evaluate the fidelity of implementation of intervention components, and clarify the causal pathway if intervention effects are found.

1c. Trial design

This study is an individually randomized controlled trial (RCT) comparing proactive care management^{30,31} to proactive care management plus MyHC-T2D.^{25,32}

2. Methods: Participants, interventions and outcomes

2a. Study setting

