2d.2 Secondary outcome measures

- Outcomes measured by Continuous Glucose Monitor, over 10 days, at baseline and 14-month assessment:
 - Percent time with biochemical hypoglycemia (<54 mg/dL);
 - Number of Level 2 biochemical hypoglycemic events (15 or more minutes <54 mg/dL).
 - Percent time biochemical hypoglycemia (< 70 mg/dL)
 - Number of level 1 hypoglycemic events (≥ 15 minutes at 54 - 69 mg/dL)
 - Number of nocturnal hypoglycemic events (≥ 15 minutes < 70 mg/dL between midnight and 6 am)
 - Percent time 70 to 180 mg/dL
 - Percent time above 180 mg/dL
 - Percent time above 250 mg/dL
 - Average blood glucoses, mg/dL
 - Standard deviation of glucose
 - Coefficient of variation for glucose (%CV)
 - Glucose management indicator
- Outcomes measured by self-report survey at baseline, 6, 10, and 14 months:
 - Number of severe hypoglycemic events in prior 4 months;
 - Hypoglycemia unawareness measured by the single item Gold survey;^{35,36}
 - Number of symptomatic⁴⁸ hypoglycemic events in the prior 4 weeks;⁴⁶
 - Fear of hypoglycemia using the Hypoglycemia Fear Survey-II;⁴⁹
 - Number of nocturnal hypoglycemia events (defined as “during sleep”) during past 6 months;⁵⁰
 - Diabetes and hypoglycemia knowledge with the revised Diabetes Knowledge Test;⁵¹
 - Diabetes self-efficacy using the 8-item Diabetes Self-Efficacy scale.⁵²

- Outcomes defined based on data collected from the EHR:
 - Hemoglobin A1c (HbA1c). The most recent HbA1c measures in the 12 months before baseline will be used for the baseline measure. Most recent measures within the past 3 months will be collected at 14 months. If the participant has not had an HbA1c within the past 3 months at 14 months, they will be asked to have one for the study.
 - Hypoglycemia-related healthcare utilization: total number urgent care, emergency department and inpatient visits for hypoglycemia as primary or principal diagnosis.

Figure 2 shows the relationship between outcome measures and study activities. Due to cost and participant burden, we will collect CGM measures only at baseline and at 14 months. We will measure all secondary outcomes including potential mediators of the intervention, at 6, 10 and 14 months after baseline assessment to identify potential early vs. later effects of the intervention.³²

Outcome Measures and Study Activities

Enrollment call,
Baseline Measures

[figure not shown]

Figure 2: Outcome measures and study activities

2e. Participant timeline

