Study data will be collected using self-report surveys at baseline, 6, 10- and 14-months; biochemical measures of percent time with hypoglycemia and number of biochemical hypoglycemic events using CGM at baseline and 14 months; and data extracted from the EHR for Hemoglobin A1c and hypoglycemia-related healthcare utilization at baseline and 14 months. The outcomes are described in section 2d, above.

4a.1 Self-report measures:

All self-report instruments are included in **Appendix C**. Survey questions will be administered at baseline and all follow up time points (6, 10 and 14 months) by telephone by trained KPHRI survey research program (SRP) staff. Telephone data collection will be performed using Sawtooth Ci3 and WinCATI computer-assisted telephone interviewing (CATI) software. SRP Interviewers are trained in standardized survey interviewing techniques, use of the CATI system, and will be trained in project-specific procedures including item-by-item specifications for each questionnaire. Interviewers' phone performance, productivity, and response rates are routinely monitored; corrective or remedial training is provided if necessary. Interview quality is continuously assessed using silent monitors installed on all telephones; completed interviews are edited and coded within 48 hours, and interviewer feedback occurs on a regular basis. SRP Interviewers are certified in NIH Human Subjects Protections.

4a.2. CGM data:

CGM data will be collected at baseline and 14 months using the Dexcom 6G Pro CGM integrated sensors and transmitters in blinded mode. We chose Dexcom sensors because of validity, reliability, ability to record glucose measurements blinded to the participant; and the ability to store up to 10 days of data. At both timepoints we will collect 10 days of CGM readings. The readings will be blinded at the time of data collection but shared with the participant at the end of the study.

Baseline CGM data will be collected after collection of baseline self-report data but before beginning any intervention activities. CGM data at 14-months will be collected at the same time as outreach for 14-month follow up self-report. In both cases the process will be the same:

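### Level 1 CGM events are counted as time inside the 54-69 mg/dL band, so one deep low can score 0, 1 or 2 and the count does not track severity

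*Combined protocol and SAP*

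**What the plan says.** Section 2d.2 (Secondary outcome measures) lists twelve CGM measures. Three are event counts:

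- Level 1, two-sided: "Number of level 1 hypoglycemic events (≥ 15 minutes at 54 - 69 mg/dL"). The trial summary table has the same band: "of events ≥ 15 minutes glucose 54-69 mg/dL".
- Level 2, one-sided, at any hour: "Number of Level 2 biochemical hypoglycemic events (15 or more minutes <54 mg/dL").
- Nocturnal, one-sided, for six hours of the day: "Number of nocturnal hypoglycemic events (≥ 15 minutes < 70 mg/dL between midnight and 6 am").

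The list also has percent time below 54 and below 70 mg/dL, the latter as "Percent time biochemical hypoglycemia (< 70 mg/dL"). Section 1b.2.a makes event reduction a key secondary superiority objective: "Reducing biochemical hypoglycemic events (CGM assessed"). On the data, section 4a.2 says: "At both timepoints we will collect 10 days of CGM readings".

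Section 4c says only that secondary outcomes are modelled by GEE with a suitable link and error distribution. Nothing states when a CGM event starts or ends, whether two band visits in one excursion are merged, or whether an excursion that reaches Level 2 is left out of Level 1. The amendment log names an international consensus as the source of the added CGM outcomes but reproduces no counting rule.

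**The concern.** A low that goes below 54 mg/dL passes through the 54-69 band twice, once falling and once rising. Whether each passage lasts 15 minutes depends on how fast glucose is moving, not on how serious the low is. The same deep low can therefore add nothing to the Level 1 count, or add two.

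This matters because section 2c.2 describes an intervention that teaches prompt treatment and recognition of subtle symptoms. One plausible effect is that lows become shallower rather than fewer. A count whose response to that change has no fixed sign is a poor basis for a claim that events were reduced, or were not. Because the derivation rule is unwritten, two analysts could also obtain different counts from the same trace.

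**Working it through.** **The plan's own figures.** Section 2f gives power for the primary outcome and for percent time below 54 mg/dL. It gives no rate, SD or effect for the Level 1 count, so there is no figure to reproduce.

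**Inputs.** From the documents: the band limits, the 15-minute minimum and the one-sided Level 2 and <70 definitions. Assumed, because the documents do not give them: excursion shape, rates of change, a 5-minute reading interval, and three consecutive readings counted as 15 minutes.

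**Step 1: threshold.** Band width = 70 − 54 = 16 mg/dL. Time per crossing = 16 / rate. A crossing lasts 15 minutes or more when the rate is at or below 16/15 = 1.07 mg/dL/min. At 0.8 mg/dL/min it lasts 20 min and counts; at 2 mg/dL/min it lasts 8 min and does not. Three 5-minute readings span only 10 min, so under that rule a crossing as fast as 16/10 = 1.6 mg/dL/min can count. The threshold itself depends on the unwritten rule.

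**Step 2: single excursions, 30 min at the nadir.**

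| Nadir | Fall / rise (mg/dL/min) | Level 1 | Level 2 | <70 |
|---|---|---|---|---|
| 48 | 2 / 2.5 | 0 | 1 | 1 |
| 48 | 0.8 / 2.5 | 1 | 1 | 1 |
| 48 | 2 / 0.8 | 1 | 1 | 1 |
| 48 | 0.8 / 0.8 | 2 | 1 | 1 |
| 58 | 2 / 2.5 | 1 | 0 | 1 |
| 58 | 0.8 / 2.5 | 1 | 0 | 1 |
| 58 | 0.8 / 0.8 | 1 | 0 | 1 |

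Only the Level 1 column changes with rate at a fixed depth.

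**Step 3: sign of the change when lows become shallower.** Let *d* be the mean Level 1 score of a deep low, between 0 and 2, and let a sustained shallow low score 1. If *k* lows move from deep to shallow, the Level 1 count changes by *k*(1 − *d*). It rises if *d* < 1, is flat if *d* = 1 and falls if *d* > 1. Take ten lows going from 6 deep + 4 shallow to 2 deep + 8 shallow:

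- both crossings fast (*d* = 0): 6×0 + 4 = 4 becomes 2×0 + 8 = 8;
- one crossing slow (*d* = 1): 6 + 4 = 10 becomes 2 + 8 = 10;
- both crossings slow (*d* = 2): 12 + 4 = 16 becomes 4 + 8 = 12.

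Level 2 goes from 6 to 2 and the one-sided <70 count stays at 10 in all three.

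**Step 4: the same shift with random crossing rates** (simulated, 30 min at the nadir):

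| Assumed rates (mg/dL/min) | Level 1: 6 deep + 4 shallow | 2 deep + 8 shallow | 2 deep + 6 shallow |
|---|---|---|---|
| 0.4-1 | 16 | 12 | 10 |
| 0.5-2 | 10.43 | 10.12 | 8.13 |
| 1-2.5 | 6.39 | 8.76 | 6.80 |
| 1.5-3 | 4.06 | 8.02 | 6.02 |

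In the last column total lows fall from 10 to 8, yet the band count still rises at the two faster ranges.

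**Step 5: no time at the nadir (pure V shape).** Shape matters too. At 0.8 mg/dL/min, a V to 50 spends 20 min in the band on each side and 2×4/0.8 = 10 min below 54, so it scores two Level 1 events and no Level 2. A V to 58 spends 2×12/0.8 = 30 min in the band and scores one. Here making the low shallower lowers the count. At 2 mg/dL/min, a V to 50 spends 8 + 4 + 8 = 20 min below 70 but scores neither Level 1 nor Level 2; a one-sided <70 count records it once.

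**The case against.** The strongest reply is that the plan does not depend on this measure. The Level 2 count is one-sided and runs over 24 hours, percent time below 54 and below 70 are both listed, and a shift from deep to shallow lows would show across them. The only CGM outcome given power in section 2f is percent time below 54. This stands, and it limits the point to one of twelve CGM measures.

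Two inferences therefore go too far. A reader might conclude that the event-reduction objective cannot be judged at all, or that every 24-hour event count shares the flaw. The Level 2 row contradicts both. What is missing is a one-sided 24-hour event count at the 70 mg/dL threshold.

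A reader might also infer that an effective intervention will raise the Level 1 count and look harmful. The documents do not support that either. Steps 3 to 5 give rises, no change and falls, according to rates and shapes that the documents do not state.

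It can also be said that both arms use the same definition, and that the cited consensus may supply a merging rule. Equal application does not help if the arms differ in the depth of lows, which is the comparison of interest. Merging band visits, or excluding excursions that reach Level 2, would remove the double count but leave the score dependent on depth. No such rule is written in any case.

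Finally, recruitment is complete and the protocol is at version 07, so replacing a listed outcome now would have a credibility cost. That stands, and it favours adding a measure over substituting one.

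**Conclusion.** The point holds as a defect of definition. Under the literal text one excursion below 54 mg/dL adds 0, 1 or 2 Level 1 events and a sustained shallow low adds 1. The count is not monotone in severity and its change cannot by itself be read as benefit or harm.

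The 0-1-2 result needs only the band width, the 15-minute minimum and the absence of a merging rule, for a single smooth excursion; oscillation around 54 could give more than two. Direction and size in this trial cannot be computed from the documents, so no percentage is offered. The tables in the working show that the sign varies and are not estimates for this population. The change is worth making because it is cheap and the result would otherwise be ambiguous, but it bears on one secondary outcome only.

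**What to change.** Before 14-month CGM data are analysed by arm:

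1. Add to sections 2d.2 and 4c a 24-hour count of excursions below 70 mg/dL lasting 15 minutes or more. Count each excursion once and close it only after 15 or more minutes at 70 mg/dL or above. State the reading interval and how many consecutive readings make 15 minutes.
2. State that this count and the Level 2 count together are used to judge the event-reduction objective in section 1b.2.a.
3. Keep the listed 54-69 band count as a descriptive row, shown beside Level 2.
4. Do not use a depth-classified Level 1 count (an excursion below 70 with no Level 2 run) as a stand-alone outcome. It removes the double count, but in the ten-low example it goes from 4 to 8 whatever the rates.

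The cost is reprocessing of stored traces, a short addition to two sections, and one late-added secondary measure that must be disclosed as such. If data by arm have already been seen, the new count should be labelled post hoc.

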- Use of fidelity assurance checklists for protocol integrity and skills to be covered in each educational session. After each session, the nurse will check each point that was covered. If a point was not covered, the nurse will plan for follow-up. This checklist will also permit calculation of the percentage of points covered. An independent Fidelity Monitoring Research Associate will review completed checklists using a standard protocol to document adherence and give formative feedback.

- Monitoring for potential drift through audio recording sessions. After 2 months of observation, the Fidelity Monitoring Research Associate will randomly review 10% of sessions, coding for intervention adherence and returning results to be reviewed in weekly supervision meetings. If nurses “drift” from protocols, we will add training and supervision and monitor until fidelity is established.

2d. Outcomes

2d.1 Primary outcome measure

We will measure number of self-reported severe hypoglycemia episodes in the past 12 months at baseline and 14 months after the baseline. We assess the primary outcome 14-months after baseline, to allow 2 months for baseline collection of CGM and intervention activities prior to the 12-month outcome window (**Figure 2**). This timing is consistent with prior studies showing that symptoms of hypoglycemia return after 3 to 4 weeks of avoiding hypoglycemia⁴⁵ and early impacts of the MyHC-T2D intervention on the percent time with glucose less < 54 mg/dL in patients with type 1 diabetes.²⁵

- Planned primary outcome: Self-report of any severe hypoglycemia episode (yes/no) in the prior 12 months assessed 14 months after baseline using a validated question from the Diabetes Care Profile: "In the past year, how many times have you had a severe low blood sugar reaction such as passing out or needing help to treat the reaction?"^{46,47}.
- Alternative primary outcome: Count of the number of self-report severe hypoglycemia episodes in the prior 12 months assessed 14 months after baseline using the validated question from the Diabetes Care Profile. We will evaluate the distribution of number of severe hypoglycemia events in the prior 12 months assessed on all participants at the baseline survey. If more than 60% of respondents report having had 2 or more severe hypoglycemia events in the prior 12 months, we will change our primary outcome to be a count of the number of severe hypoglycemia events in the prior 12 months.

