We estimate 256 patients (128 randomized to proactive care management, and 128 randomized to MyHC-T2D) will consent and complete the baseline survey. To account for loss to follow-up, we assume an 80% response rate for the primary outcome measured at 14-months, for an analytic sample size of 204 (102 per group). Power calculations for comparing two independent proportions and assumed a 0.05 type I error rate. Assuming 60% of patients in the proactive care management group will self-report having had a severe hypoglycemia event in 12-month look back (yes/no), we have 90% power to detect a 22.6% absolute difference between groups (i.e. 37.4% severe hypoglycemia rate in MyHC-T2D arm) for the primary outcome. We have 80% power to detect an absolute difference of 19.7% between groups. Our study has power to detect a meaningful difference (30% or more reduction in frequency of self-reported severe hypoglycemia events).⁵⁴ Other studies including for the original *my hypo compass* have similar or larger effects on severe hypoglycemia reductions.²⁵⁻²⁹ We also have 80% power to detect a 1.4% difference and 90% power to detect a 1.6% difference between groups in the secondary outcome of the percent time with biochemical hypoglycemia (<54 mg/dL); this difference is consistent with the effect seen with the original *my hypo compass*.^{25,32}

2g. Recruitment

We will recruit the study population in two steps.

Step 1, Automated risk stratification: We will identify a cohort of adults (≥ 18 years) with T2D receiving primary care at KPWA. We will identify all individuals with either a current prescription for insulin or who have intermediate-to-high risk for a SH event based on our hypoglycemia risk-stratification tool.

Step 2, Phone screening for verbal consent and to identify patients at highest SH risk: We will mail eligible participants an invitation with study brochure and notification that staff will call them about the study. KPHRI Survey Research Program (SRP) members will then call the potential participant to explain the study, assess eligibility and interest, and conduct informed verbal consent with those who are eligible and interested. We expect 1001 eligible. Based on a similar recruitment⁵⁵ and participation in other diabetes education trials, we anticipate at least 25% will consent and complete baseline data collection.⁵⁶

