- **EHR data** will be extracted by the study programmer from automated administrative and EHR data sources, including the KPHRI Data Warehouse, a research-centric repository of datasets maintained by the Research Institute. Data are stored in Teradata, SQL Server, and SAS format and cover enrollment, demographics, diagnoses and procedures, vital signs, pharmacy, lab tests, costs. A rich collection of powerful SAS macros can be used in conjunction with the KPHRI data. KPHRI data warehouse content and usage are documented by a wiki-based system authored by the data warehouse's architects, managers, and users. Access and security for electronic data sources are described below in Section 3. Ethics and Dissemination, Confidentiality.

4c. Statistical methods

Comparative effectiveness analyses will apply intent-to-treat principles, with study participants analyzed based on randomization group, regardless of intervention received. To assess comparability across study groups, we will summarize demographic characteristics and responses to baseline surveys in the two comparison groups. The preliminary analysis plan defines the primary outcome as a binary indicator for whether or not (yes/no) the participant self-reported having had a severe hypoglycemia event in the prior 12-months, assessed 14 months after baseline. We will estimate relative risk of severe hypoglycemia in the MyHC-T2D group vs. proactive care management group by fitting a modified Poisson regression model with the binary self-report measure as the dependent variable and randomization group as the independent variable. Models will adjust for age, sex, risk score, and the number of self-reported severe hypoglycemic events in the 12 months prior to baseline. Models will be fit using generalized estimating equations (GEE) and robust variance estimation to account for correlation due to patient clustering in the intervention arm within group training session cohorts, and the misspecified mean-variance relationship in using Poisson regression for a binary outcome.

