Prior to conducting analysis of 14-month outcomes, we will look at the baseline distribution of the self-reported number of severe hypoglycemic events in the prior 12-months collected at baseline. If more than 60% of enrolled patients report 2 or more events, we will revise the primary outcome to be defined as the self-reported *number* of severe hypoglycemic events in the past 12-months, measured at 14-months post baseline (a count rather than a binary outcome and fit a Poisson regression model to estimate the rate ratio for severe hypoglycemia events for the MyHC-T2D group relative to the care management group. We will assess model fit, and consider zero-inflated models as an alternative, if the number of participants reporting zero events violates distributional assumptions of the Poisson model. If primary analyses use the binary outcome measure (i.e. fewer than 60% of patients report 2 or more events in the 12-months prior to baseline), but 40% or more of respondents report 2 or more events at 14-months, we will do a secondary analysis with the count variable as the outcome.

Generalized linear regression models estimated with GEE and robust sandwich errors will also be used to estimate intervention effects on secondary outcomes, with link function and error distribution appropriate for each outcome. For secondary outcomes measured at multiple follow-up time points (6-, 10- and 14-months post-baseline), we will fit a single regression model that includes outcome measures from all follow-up time points. Models will include indicator variables for time, intervention group, and interaction terms between these variables, to estimate intervention effects at each time point. Models will adjust for age, sex, risk score and the baseline measure of the outcome. For hypoglycemia-related health care utilization (urgent care and emergency department visits, hospital admits), we will follow a similar analytic plan as the primary outcome, including the process to determine whether to model these outcomes as binary or count variables.

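### The model for severe events in the prior 4 months could also use the 12-month count already taken at baseline: an optional precision gain, not an error

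*Combined protocol and SAP*

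**What the plan says.** Section 2d.2 lists "Number of severe hypoglycemic events in prior 4 months" among "Outcomes measured by self-report survey at baseline, 6, 10, and 14 months". Section 4c plans, for outcomes with several follow-up times, that "we will fit a single regression model that includes outcome measures from all follow-up time points", with time, arm and time-by-arm terms. The covariate rule for these secondary models is "Models will adjust for age, sex, risk score and the baseline measure of the outcome". For this outcome the last item is the 4-month count at baseline.

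A longer record of the same events exists. Section 2d.1 says "We will measure number of self-reported severe hypoglycemia episodes in the past 12 months at baseline and 14 months after the baseline", and section 4c gives the primary model this covariate set: "Models will adjust for age, sex, risk score, and the number of self-reported severe hypoglycemic events in the 12 months prior to baseline". Section 3a places baseline data collection before randomization, so both counts are pre-randomization covariates. Section 4c names baseline severe-hypoglycemia history for the secondary models only in the exploratory interaction analyses, not as a main adjustment term.

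**The concern.** A 4-month count of severe events is short and therefore a noisy marker of how often a person has them. The 12-month count covers those 4 months and 8 more, comes from the same baseline survey, and is already judged worth adjusting for in the primary model. Leaving it out of the 4-month model may give a wider confidence interval than the collected data allow. The documents state no power for this outcome, so any free precision is welcome. Only efficiency is at stake. The randomized comparison is unbiased with or without the extra term, and the primary analysis is untouched.

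**Working it through.** **1. The plan's own figure.** Section 2f gives an "analytic sample size of 204 (102 per group"), from 256 × 0.80 = 204.8. With two-sided alpha 0.05, power = Φ{[d√n − 1.96√(2p̄(1−p̄))] / √(p₁q₁ + p₂q₂)}.
- 60% v 37.4%: (0.226 × 10.10 − 1.96 × 0.707) / 0.689 = 1.30, power 90.4% (stated 90%).
- 60% v 40.3%: (0.197 × 10.10 − 1.96 × 0.707) / 0.693 = 0.87, power 80.8% (stated 80%).

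Both reproduce. They concern the binary primary outcome. For the 4-month count the documents give no mean, dispersion or correlation, so everything below rests on assumptions.

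**2. Window arithmetic.** (12 − 4)/12 = 2/3 of the look-back months lie outside the 4-month count. This is a share of calendar time, not of prognostic information.

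**3. Closed form, each person's rate perfectly stable (favorable case).** Assume gamma-Poisson counts with shape k and yearly mean m, set so that P(no event in 12 months) = (1 + m/k)^(−k) = 0.40, using the 60% in section 2f. Let μ = m/3 and v = μ²/k. Then R² of a later 4-month count is:
- on the 4-month baseline count: v²/(μ+v)²
- on both counts: 3v²/[(μ+3v)(μ+v)] (with a stable rate the 12-month total carries all the information)

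For k = 1: m = 1.5, μ = 0.5, v = 0.25. R² is 0.0625/0.5625 = 0.111 and 0.1875/0.9375 = 0.200. The variance ratio is 0.800/0.889 = 0.900, and the SE falls by 1 − √0.900 = 5.1%.

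| k | m | R², 4-month | R², both | Variance ratio | SE falls | Patients for equal precision (v 204) |
|---|---|---|---|---|---|---|
| 0.3 | 6.06 | 0.758 | 0.830 | 0.704 | 16.1% | 144 |
| 0.5 | 2.62 | 0.405 | 0.535 | 0.782 | 11.6% | 160 |
| 1 | 1.50 | 0.111 | 0.200 | 0.900 | 5.1% | 184 |
| 2 | 1.16 | 0.026 | 0.060 | 0.966 | 1.7% | 197 |

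**4. Closed form, rates drifting.** The baseline and month-14 windows are 14 months apart, or 14/4 = 3.5 four-month steps. A correlation of 0.8 per step leaves 0.8^3.5 = 0.46. For k = 1, R² on the 4-month count becomes 0.111 × 0.46² = 0.023, and 0.033 with both counts. Over the four shapes the SE falls by only 0.2% to 0.6%. At 0.6 per step it falls by less than 0.1%.

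**5. Simulation on the model scale.** Poisson log-link, robust SE, one follow-up time, n = 204, assumed rate ratio 0.7, 600 replicates. Entries are the empirical SD of the log rate ratio with the 4-month count alone → with both counts, and the variance ratio in brackets.

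| k | Rate correlation | Raw counts | log(1 + count) |
|---|---|---|---|
| 0.5 | 1 | 0.227 → 0.230 (1.03) | 0.197 → 0.179 (0.83) |
| 1 | 1 | 0.278 → 0.266 (0.92) | 0.274 → 0.261 (0.91) |
| 2 | 1 | 0.263 → 0.261 (0.98) | 0.263 → 0.258 (0.96) |
| 0.5 | 0.6 | 0.244 → 0.245 (1.01) | 0.242 → 0.238 (0.97) |
| 1 | 0.6 | 0.280 → 0.280 (1.00) | 0.278 → 0.277 (0.99) |
| 2 | 0.6 | 0.272 → 0.274 (1.01) | 0.273 → 0.273 (1.00) |

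Coding matters. In the first row, raw counts gave no smaller SD, while log coding raised power from 43% to 51% (Monte Carlo error about 2 points).

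**6. Simulation with a risk covariate in the model.** Adding log(1 + 12-month count) to log(1 + 4-month count) gave variance ratios of 0.83 to about 1.0. With a correlation of 0.8 over the whole baseline-to-follow-up interval, the variance fell by about 1% to 6%. In SE terms, 1 − √0.83 = 8.9%, 1 − √0.94 = 3.0% and 1 − √0.99 = 0.5%. In patients, 204 × 0.83 = 169, 204 × 0.94 = 192 and 204 × 0.99 = 202. With heavy recall error in the 12-month answer, adding it gave ratios of 0.97 to 1.01, so the extra term costs essentially nothing. Replacing the 4-month term by the 12-month term gave ratios up to 1.32 under such error.

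**The case against.** The strongest reply is that nothing here is wrong. Adjusting each secondary outcome for its own baseline value is standard, uniform across outcomes and unbiased. That stands in full.

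Several stronger readings are tempting, and the documents do not support them:
- A reader might infer that the model adjusts for nothing but the 4-month count. It also includes age, sex and risk score, and risk score may absorb part of any gain.
- A reader might infer that two thirds of the known history is thrown away. That is a fraction of months. The counts overlap, and the information gained is smaller (R² 0.111 to 0.200 at k = 1 with a stable rate).
- A reader might infer that precision is definitely lost. No documented figure shows this, and plausible scenarios give no gain.
- A reader might infer that this is the trial's only measure of event frequency. Section 4c makes the 12-month count the primary outcome if more than 60% report 2 or more events at baseline, and provides a conditional secondary analysis of it.

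Two further replies have force. In a simulation with selection for eligibility, about 64% had 2 or more baseline events at shape 0.3. That passes the 60% trigger, so where rates vary most the primary outcome would itself become a count adjusted for the 12-month history. And the gain depends on coding: in a separate set of 12 raw-count scenarios the variance ratio was 0.944 to 1.003, and 0.98 or above in 9 of them.

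What survives is narrow. A pre-randomization covariate already in hand is left out of one model where it can help and, coded sensibly, hardly hurts.

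**Conclusion.** This holds as an optional efficiency improvement to one secondary outcome. The planned analysis is valid, the sections do not contradict each other, and the primary analysis is unaffected. Under assumed gamma-Poisson rates and log(1 + count) coding, the variance of the month-14 log rate ratio falls by about 0% to 17% (SE by up to about 9%). At a baseline-to-follow-up correlation of 0.8 the variance falls by about 1% to 6%. The gain is near zero when people have similar rates, when rates are unstable or when recall is poor, and mostly little or nothing with raw counts. The simulations did not include clustering by training session or the joint 6-, 10- and 14-month GEE model, and the result moves with the assumed shape and with how the correlation is defined.

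**What to change.** In section 4c, add one sentence for this outcome only: besides age, sex and risk score, the model includes both the baseline 4-month count and the baseline 12-month count of severe events, each entered as log(1 + count).

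Two variants should be avoided. Subtracting the 4-month answer from the 12-month answer can give negative values when a participant's recall is inconsistent, and log(1 + count) is undefined at −1 or below. Dropping the 4-month term can lose precision if the 12-month answer is poorly recalled.

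The wording should be fixed before outcomes are compared by arm, so that the choice cannot look data-driven. If that point has passed, the planned model should stay as the main analysis and this one be reported beside it as a sensitivity analysis. The cost is one line of text and one extra model term. No new data are needed.
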